13. INTERIM ANALYSES

No interim analysis will be performed in this study.

14. CHANGES IN STUDY CONDUCT OR PLANNED ANALYSIS

Because the study was prematurely terminated as noted in Section 3, pharmacokinetic, exploratory, sensitivity, as well as some safety analyses will not be completed under this SAP.

Additionally, the definition of the Evaluable population (section 7.2) has been revised from the study protocol (section 14.3.2) because "planned doses" were a function of the treatable BSA and the weight of the tubing and caps biased the calculation. So, a simple 80% threshold would have excluded all of the N subjects. Therefore, compliance is computed with consideration of the weight effect of the bottles with the compliance threshold set as greater or equal to 20%.

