14.3.2 Evaluable Populations

Inclusion of a subject in either of the evaluable populations below requires that the subject complete $\geq 80\%$ of all planned doses of Clobetasol Topical Oil. The determination that a subject met this requirement will be primarily on the basis of the subject diary, along with observation by the study staff of the final dose which is administered at the End of Treatment visit. However, if the weight of the subject's returned supplies of study drug suggests noncompliance with study drug administration, the study team may judge a subject not to be evaluable for the purposes of inclusion in the evaluable populations described below and/or the purposes of achieving ≥ 20 evaluable subjects within each cohort.

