14.3.2.1 HPA Axis Function

The evaluable population for HPA axis function will include all subjects:

1. Who completed the study without any major protocol deviations (e.g., deviations of the inclusion/exclusion criteria, or use of a prohibited medication), as determined by the study team;
2. Who were compliant with study drug use, defined as completion of $\geq 80\%$ of all planned doses of Clobetasol Topical Oil including 100% of the last 5 doses (including the final dose administered at the End of Treatment visit), as determined by the study team; and
3. Whose HPA axis suppression tests were evaluable (i.e., blood samples were able to be analyzed and results reported).

14.3.2.2 PK

The evaluable population for PK analyses will include all subjects:

1. Who completed the study without any major protocol deviations (e.g., deviations of the inclusion/exclusion criteria, or use of a prohibited medication), as determined by the study team;
2. Who were compliant with study drug use, defined as completion of $\geq 80\%$ of all planned doses of Clobetasol Topical Oil including 100% of the last 5 doses (including the final dose administered at the End of Treatment visit), as determined by the study team; and
3. Whose PK blood samples were taken within the required windows and processed without any known problems according to the instructions provided by the analytical laboratory.

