7.2 Evaluable Population

The Evaluable population will be defined as subjects:

- 1) who met all inclusion/exclusion criteria, and did not report use of a prohibited medication;
- 2) who during the study period used $\geq 20\%$ of study drug dispensed, based on the weight effect of the bottles, calculated as $[(\text{total (drug dispensed (g)} - \text{drug returned (g))}) / 120 \text{ g dispensed}] * 100$, as recorded on study drug accountability CRF; and
- 3) who based on data reported on the study drug missed doses CRF were compliant with the last 5 doses (including the final dose administered at the End of Treatment visit).

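### The SAP replaces the protocol's 80% dose count with a fixed 24 g bottle-weight cut-off, without explaining why the diary count was dropped or how 20% was chosen

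*SAP*

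**What the plan says.** **Protocol.** Section 14.3.2 makes 80% of planned doses a condition of either evaluable population and names the evidence: "The determination that a subject met this requirement will be primarily on the basis of the subject diary", together with staff observation of the last dose. Bottle weight is secondary. If returned supplies suggest noncompliance, "the study team may judge a subject not to be evaluable for the purposes of inclusion in the evaluable populations described below". Section 14.3.2.1 repeats the rule for HPA function as at least 80% "of all planned doses of Clobetasol Topical Oil including 100% of the last 5 doses".

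**SAP.** Section 7.2 requires instead at least 20% "of study drug dispensed, based on the weight effect of the bottles", computed as grams dispensed minus grams returned, divided by 120 g. A separate criterion keeps the end-of-treatment rule, admitting subjects "who based on data reported on the study drug missed doses CRF were compliant with the last 5 doses". Section 14 discloses the change. It says that planned doses "were a function of the treatable BSA and the weight of the tubing and caps biased the calculation", and adds: "So, a simple 80% threshold would have excluded all of the N subjects". It concludes: "Therefore, compliance is computed with consideration of the weight effect of the bottles with the compliance threshold set as greater or equal to 20" percent. Section 9 still tabulates subjects who were at least 80% compliant and does not say how that is measured.

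**The concern.** The protocol rule counts applications; the SAP rule measures mass. They agree only if every subject uses about the same grams per application, and the protocol gives no reason to expect that. Section 13.3 tells subjects to use just enough to cover the designated areas, up to about 3.5 g, and Cohort 1 admits roughly 25% to 50% BSA.

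The stated reasons do not fill the gap. Cap and tubing weight can bias a weight but not a diary count. A number of planned doses does not depend on BSA. A planned amount does, but a fixed 120 g denominator does not adjust for it.

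At stake is the Evaluable column of Table 14.3.6.2, which readers will take to describe adequately treated subjects under maximal use. As written, it may include under-dosed subjects or exclude adherent ones.

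**Working it through.** **Inputs from the documents.** Twice-daily dosing and a ceiling of about 3.5 g per application (Protocol 13.3); End of Treatment on Day 15 or 16, with one dose on site (Protocol 10.3); about 60 g per bottle (Protocol 13.6.1); a 20% threshold and 120 g denominator (SAP 7.2).

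**Assumptions.** Grams per dose below 3.5 g, and any container weight T per bottle left uncorrected. The documents give neither.

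**The plan's own figure.** Two bottles × 60 g = 120 g, and 0.20 × 120 = 24 g. The 20% itself cannot be reproduced, because no derivation is given.

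**Protocol rule in doses.**
- Day 15 visit: 14 × 2 + 1 = 29 planned; 0.8 × 29 = 23.2, so at least 24 (82.8%).
- Day 16 visit: 15 × 2 + 1 = 31 planned; 0.8 × 31 = 24.8, so at least 25 (80.6%).

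**SAP rule in doses (29 planned).** If container weight cancels, the doses needed are 24/g, rounded up. If the returned weight includes a container of T grams that the dispensed weight omits, true use must reach 24 + 2T. The T that makes this equal 24 doses is (24g − 24)/2.

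| Grams per dose (g) | Doses reaching 24 g, container cancels | T at which 24 g equals 24 doses |
|---|---|---|
| 3.5 (ceiling) | 24/3.5 = 6.86, so 7 (24.1%) | 30 g |
| 1.75 (assumed) | 24/1.75 = 13.7, so 14 (48.3%) | 9 g |
| 1.0 (assumed) | 24/1.0 = 24 (82.8%) | 0 g |

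If container weight cancels, 24 g equals exactly 80% of doses only at 24/23.2 = 1.03 g per dose. Below 24/29 = 0.83 g per dose, even a fully adherent subject fails.

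**Can one container weight rescue the cut-off?** Suppose grams scale with treated area and 3.5 g covers 50% BSA. Then 25% BSA takes 3.5 × 25/50 = 1.75 g, and Cohort 1 spans the first two rows.
- T = 9 g: true use needed is 24 + 18 = 42 g. At 1.75 g this is 42/1.75 = 24 doses, as the protocol intends. At 3.5 g it is 42/3.5 = 12 of 29 (41.4%).
- T = 30 g: true use needed is 24 + 60 = 84 g. At 3.5 g this is 24 doses. At 1.75 g it is 84/1.75 = 48, more than the 29 planned.

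No single T fits both ends. In every case the subject must also meet the last-5-doses rule, which says nothing about earlier doses.

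**Would 80% by weight exclude everyone?** It needs 0.8 × 120 = 96 g of recorded use.
- Full adherence at the ceiling gives 29 × 3.5 = 101.5 g, so 96 g is out of reach once 2T exceeds 5.5 g, that is, T above 2.75 g. For 31 doses, 108.5 − 96 = 12.5 g, so T above 6.25 g.
- With no container bias, a fully adherent subject still needs 96/29 = 3.31 g per dose, 95% of the ceiling.

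The SAP's statement is therefore credible for a weight-based 80%. It shows nothing about a diary-based 80%.

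**The case against.** The change is disclosed, names the section it alters and gives reasons. Weight has a place in the protocol, as grounds for judging a subject non-evaluable. If a dose means an amount, a diary cannot measure it, so the BSA remark partly explains the move to weight. A lower threshold is also a sensible response to a constant weighing bias.

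The numerical illustrations rest on assumptions. Only the 3.5 g ceiling is documented, and it is not tied to any BSA. Protocol 11.11 has each bottle weighed before dispensing and after return, so as planned the container cancels. The 30 g case would give a fully adherent 1.75 g subject a recorded use of 50.75 − 60 = −9.25 g, which is implausible and would be obvious in the accountability data. The last-5-doses rule protects exposure just before the HPA test. A diary was planned, but nothing shows that it was completed. With 8 subjects the column is imprecise anyway: even 0 of 8 suppressed has an exact two-sided 95% upper limit of 1 − 0.025^(1/8), about 37%.

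Much of this stands as a limit on size. The 30 g case shows only that no container weight reconciles the two rules; it is not a likely outcome. But the central gap remains. No stated reason explains why dose records serve for the last 5 doses and not for the whole course, 20% has no derivation, and reading a dose as an amount does not justify one denominator for all subjects.

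**Conclusion.** The concern holds, as a minor point. The 24 g cut-off does not represent 80% of planned doses when grams per dose differ between subjects, and the SAP justifies neither the switch from the diary nor the 20%. That conclusion needs no assumed figures. The size does: with container weight cancelling, the cut-off ranges from 24% of doses at the documented ceiling to 83% at an assumed 1.0 g.

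The number of subjects misclassified and the direction of any effect on the suppression percentage cannot be determined from the documents. At most 8 subjects and one secondary column are involved. The Safety-population HPA result is unaffected, the cohort-progression rule uses that population, and no later cohort was enrolled. Because SAP 6 lists all collected data, a reader could reapply the protocol rule if the dose records are complete.

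**What to change.** - **SAP 7.2, criterion 2:** restore at least 80% of planned doses, counted from the diary-based application and missed-dose data (Listings 16.2.5.1 and 16.2.5.3), after confirming that they cover the whole treatment period. If they do not, say so. Keep the last-5-doses criterion.
- **Weight check:** retain the protocol's discretionary check, documenting each exclusion and its reason. Report net grams used descriptively, tare-corrected where the two weighings are not like for like.
- **SAP 9 and Table 14.1.1:** define the 80% row by the same dose count.
- **Any 20% weight-based set:** show it only as a labelled post hoc supplement, with the tare value and the derivation of 20%.
- **SAP 14:** state why the diary count was dropped and whether cortisol results were known when 20% was chosen. Protocol 14.4 requires SAP approval before any analyses; the documents do not otherwise address this, and nothing in them indicates that the results influenced the choice.

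The cost is SAP wording and one recalculated flag for at most 8 subjects, using records that the SAP already plans to list. The Evaluable population may become smaller or larger.

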15. REFERENCES

N/A

16. PRESENTATION OF DATA

16.1 Tables

The Tables are numbered in accordance with the ICH standard numbering conventions.

Number	Description	Analysis Population
Table 14.1.1	Subject Disposition	Safety Population
Table 14.1.3	Demographic Summary	Safety Population
Table 14.3.1.1	AE Summary	Safety Population
Table 14.3.1.2	Summary of All TEAEs by MedDRA System Organ Class: Severity and Relatedness	Safety Population
Table 14.3.6.1	Laboratory Values by Visit	Safety Population

Table 14.3.6.2	HPA Axis Suppression by Visit	Safety Population, Evaluable Population
----------------	-------------------------------	---

16.2 Listings

The Listings are numbered in accordance with the ICH standard numbering conventions.

Number	Description	Analysis Population
Listing 16.2.1	Subject Disposition	Safety Population
Listing 16.2.2	Protocol Deviations	Safety Population
Listing 16.2.4.1	Subject Demographics	Safety Population
Listing 16.2.4.2	Inclusion/Exclusion Criteria	Safety Population
Listing 16.2.4.3	Medical History	Safety Population
Listing 16.2.5.1	Study Drug Application	Safety Population
Listing 16.2.5.2	Study Drug Accountability	Safety Population
Listing 16.2.5.3	Study Drug Missed Doses	Safety Population
Listing 16.2.5.4	PK Sampling	Safety Population
Listing 16.2.6	HPA Axis Suppression	Safety Population
Listing 16.2.7	Adverse Events	Safety Population
Listing 16.2.8.1	Safety Lab Testing - Hematology	Safety Population
Listing 16.2.8.2	Safety Lab Testing - Chemistry	Safety Population
Listing 16.2.8.3	Urine Pregnancy Test	Safety Population
Listing 16.2.9.1	Abbreviated Physical Exam	Safety Population
Listing 16.2.9.2	Tolerability Assessments	Safety Population
Listing 16.2.9.3	Atopic Dermatitis Assessment	Safety Population
Listing 16.2.10.1	Prior and Concomitant Medications	Safety Population
Listing 16.2.10.2	Prior and Concomitant Non-Drug Treatment	Safety Population

17. APPENDICES

N/A
